6.5 Primary Patency for ATK subjects only (as measured by DUS Core Lab)

Primary patency of the target lesion for ATK subjects will be reported through 12 months at 30 days, 6 months, and 12 months using Target Lesion DUS Stenosis category (recorded from the 'Core Lab Analysis – DUS Image Findings' CRF page). Primary patency for ATK subjects will be analyzed by subject.

Evaluable subjects: To be included in the denominator at a particular visit, the subject should have had a valid stenosis category result (patent, 50-99%, or occluded) in the DUS for the visit (23 - 37 days for 30 days, 150 - 210 days for 6 months, and 335 - 395 days for the 12 months), or the last DUS result prior to the respective visit indicates failure, or the subject should have had a TLR event before the upper limit of visit window (37 days for 30 days, 210 days for 6 months, and 395 days for the 12 months).

*Note:

a) If a subject misses the respective visit or does not have valid DUS result for the respective visit, yet the DUS result in the next visit is patent and the subject has no TLR by the next visit date, then the subject is evaluable and will be counted as success.

b) If a subject misses the respective visit or does not have valid DUS result for the respective visit, and the last DUS result prior to the respective visit indicates failure, and there is no DUS result on subsequent visits to indicate patency, then the subject is evaluable and will be counted as failure.

c) If a subject misses the respective visit or does not have valid DUS result for the respective visit, has no TLR prior to the respective visit, and does not meet the conditions specified in a) and b) above, then the subject is not evaluable.

Primary patency for ATK subjects is based on the following definition:

Primary patency of the target lesion duration = (The earlier date of (Date of Imaging DUS/TLR date) - Date of Index Procedure)

Failure: Subject has a failure event if the stenosis category for Target Lesion as adjudicated by Core Lab DUS is occluded or 50-99%, or TLR has occurred before the upper limit of visit window (as per section 6.2), or as indicated in the *Note section b) above.

Success: Subject has no failure event and is an evaluable subject as defined above, or as defined in *Note section a).

Kaplan-Meier:

Becton Dickinson and Company	Confidential	Page 13
Protocol BPV-16-001	Statistical Analysis Plan	Jan 12, 2022

In addition to the analyses that are proportion-based, survival analysis will be performed (Kaplan-Meier estimate of survival function). Primary patency of the target lesion for ATK subjects at 30 days, 6 months, and 12 months, the time to first event will be the time from index-procedure to the first occurrence of the first failure event, all subjects who have succeeded the primary patency endpoint will be censored at Day 395 if not discontinued (discontinued subjects will be censored at discontinuation day), and all the subjects with missing primary patency endpoint will be censored at the last available study day.

Binary outcome and Kaplan-Meier analyses for ATK subjects will be provided for the ITT population.

6.6 Restenosis for ATK Subjects Late for More Than 30 Days at 12-Month Visit due to COVID-19 (as measured by DUS Core Lab)

Restenosis of the target lesion for ATK subjects late for more than 30 days at 12-month visit due to covid-19 will be reported using Target Lesion DUS Stenosis category (recorded from the 'Core Lab Analysis – DUS Image Findings' CRF page) by subject.

Evaluable subjects: To be included in the denominator, the subject should have been late for more than 30 days at the 12-month visit (more than 395 days since index procedure) due to COVID-19 (identified via Protocol Deviation and Study Visit CRFs) and had a valid stenosis category result (patent, 50-99%, or occluded) in the DUS for the visit.

Restenosis: Subject has restenosis if the stenosis category for Target Lesion as adjudicated by Core Lab DUS is occluded or 50-99%.

7 Statistical Analysis of Subgroup Analyses

7.1 Primary and Secondary Endpoints for Above the Knee (ATK) and Below the Knee (BTK) subjects

The primary and secondary endpoints will be presented descriptively for ATK and BTK subjects. The endpoints and statistical methods will be similar to section 5 and section 6.

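### SAP 6.5 can score a 6-month primary patency success after a core-lab scan has already shown restenosis, while the Kaplan-Meier analysis in the same section counts that subject as failed

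*SAP*

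**What the plan says.** SAP 6.5 defines primary patency for ATK subjects at 30 days, 6 months and 12 months from the core-lab DUS category and TLR. Five parts matter here.

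- **Evaluable.** A subject enters a visit's denominator with a valid scan in the window, with a TLR before the window closes, "or the last DUS result prior to the respective visit indicates failure".
- **Note a).** A missed or invalid visit is a success if "yet the DUS result in the next visit is patent and the subject has no TLR by the next visit date". Earlier scans are not mentioned.
- **Note b).** For a missed or invalid visit, a failing most recent scan is carried forward only if "there is no DUS result on subsequent visits to indicate patency". Note c) makes the remaining missed visits without TLR not evaluable.
- **Failure and Success.** The DUS part of the Failure line reads: "Subject has a failure event if the stenosis category for Target Lesion as adjudicated by Core Lab DUS is occluded or 50-99" per cent. It has no time reference, whereas the TLR part is tied to the upper limit of the visit window. Success reads: "Subject has no failure event and is an evaluable subject as defined above, or as defined in *Note section a". Note a) is thus an alternative route to success that does not itself require the absence of a failure event.
- **Kaplan-Meier.** "the time to first event will be the time from index-procedure to the first occurrence of the first failure event". The same paragraph adds that "all subjects who have succeeded the primary patency endpoint will be censored at Day 395 if not discontinued".

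**The concern.** The Kaplan-Meier rule treats loss of primary patency as permanent: the first failing scan or TLR is the event, and nothing later removes it. The binary rules in the same section do not. Note a) looks forward to the next scan and never back, and Note b) expressly gives way to a later patent scan. A subject can therefore be a failure at 30 days and a success at 6 months with no re-intervention between.

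Two things are at stake. The two planned estimates of one endpoint can classify the same subject differently. And because the DUS part of the Failure sentence is undated, two programmers working from this text could report different 12-month binary rates. SAP 7.2 and 7.3.2 reuse these definitions in adjunctive-treatment and DCB subgroups, where each subject weighs more.

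**Working it through.** The plan states no expected patency rate, power or sample-size calculation, so there is no figure of its own to reproduce. The check applies the rules to every possible scan history.

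**Inputs.** Three scheduled scans, at 30 days, 6 months and 12 months (Protocol 6.4). About 175 ATK subjects (Protocol 3, SAP 3.3). Rules from SAP 6.5. No TLR assumed.

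**Method.** Code each scan as P (patent), F (50-99% or occluded) or M (missed or invalid). This gives 3 × 3 × 3 = 27 sequences. At each visit, compare the binary status with the Kaplan-Meier first-failure status, under two readings of the undated Failure sentence: failure at that visit only (per visit), or failure at any visit so far (cumulative).

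**Visits where Kaplan-Meier already has an event but the binary result is not failure:**

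| Sequence (30 d, 6 m, 12 m) | Per-visit reading | Cumulative reading |
|---|---|---|
| F-M-P | success at 6 m (Note a) and 12 m | success at 6 m (Note a); failure at 12 m |
| F-P-M | success at 6 m; not evaluable at 12 m | failure at 6 m; not evaluable at 12 m |
| F-P-P | success at 6 m and 12 m | none |
| F-P-F | success at 6 m | none |
| P-F-P, F-F-P, M-F-P | success at 12 m | none |

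**F-M-P at 6 months.** The failing 30-day scan makes the subject evaluable. Note b) does not apply, because the 12-month scan is patent. Note a) applies and scores a success. On the cumulative reading the general Failure sentence also catches this subject, so the outcome follows from giving the specific note precedence; without that precedence, the section assigns both outcomes. On that reading the subject is then a 12-month failure despite a patent 12-month scan.

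**Reach of Note a).** F-M-P is the only sequence in which Note a) overrides an earlier failure. The 30-day visit has no earlier scan, and the 12-month visit has no later scheduled scan.

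**F-P-M at 12 months.** The most recent scan is patent, so neither the evaluable clause nor Note b) applies. Note c) removes the subject from the denominator under both readings.

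**Weight of one subject.** Moving one evaluable subject from success to failure lowers a rate by 1/n: 1/175 = 0.57 points, 1/140 = 0.71, 1/100 = 1.00. The values of n below 175 are assumptions. Returning one F-P-M subject to the denominator lowers a rate p by p − pn/(n+1) = p/(n+1), which is less than 1/n.

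**How many F-M-P subjects.** The documents give no rates. Three conditions must all hold. Assume 4% fail at 30 days, 10% of those miss the 6-month scan, and 15-30% of those are patent at 12 months.

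- First two conditions: 175 × 0.04 × 0.10 = 0.7 subjects.
- All three: 0.7 × 0.15 = 0.1 to 0.7 × 0.30 = 0.2 subjects.
- Doubling both of the first two assumptions multiplies this by 4, giving 0.42 to 0.84 subjects.

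**The case against.** The strongest defence is that a later patent scan may show the failing reading to have been wrong, so letting it prevail could be a reasonable design choice. Part of this stands: a permanent-failure rule locks in any single false failing scan and biases patency downward in those subjects. But the SAP gives no such rationale, the rules correct in one direction only, and the Kaplan-Meier rule would still count the failure. A core-lab re-read is the more direct remedy for a doubtful scan.

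A second defence concerns scale: this is a descriptive secondary endpoint, with no hypothesis (Protocol 7.1) and no statistical basis for the sample size (SAP 3.3). That stands. No test, error rate or decision threshold is affected.

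A reader might go further and infer that the rules inflate 12-month patency, or that Note b) lets any later patent scan cancel an earlier failure. The documents do not support this as a stated result. Notes a) and b) govern only missed or invalid visits, so neither applies to a valid 12-month scan. Several features lean cumulative: patency is reported through 12 months, the main Success route requires the absence of a failure event, and a prior failing scan can carry evaluability forward. A 12-month effect needs the per-visit reading, which the text permits but does not state. Nor is a TLR cancelled, since Note a) requires none by the next visit.

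Finally, the Kaplan-Meier side is not airtight. The clause censoring successful subjects at Day 395 does not tie success to a visit and could be misapplied to an F-M-P subject. The first-failure wording is the natural governing rule, but the SAP should say so.

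**Conclusion.** The point holds in a limited form. Note a), with the exception in Note b) and the alternative route in the Success line, produces a 6-month binary success in a subject whom the first-failure Kaplan-Meier rule counts as failed from the 30-day scan. This is an inconsistency in stated rules and arises on either reading of the Failure sentence, taking the specific note over the general sentence.

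Through Note a) it reaches only the 6-month rate, probably in about one subject or fewer, at 0.57 points per subject if all 175 ATK subjects are evaluable. That count rests on assumed rates.

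Whether the 12-month rate is affected is open. If the Failure sentence is per visit, five sequences (F-M-P, F-P-P, P-F-P, F-F-P, M-F-P) are 12-month successes despite a Kaplan-Meier event; the documents do not allow the size to be estimated. If it is cumulative, none is. On both readings F-P-M leaves the 12-month denominator despite a documented failure.

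**What to change.** Amend SAP 6.5 as follows.

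1. Add to Note a): *and no earlier core-lab DUS was 50-99% or occluded*.
2. Delete the later-patency exception from Note b).
3. In the evaluable clause and Note b), refer to any prior DUS result showing failure, not only the most recent one.
4. Add to the Failure line: *once a core-lab DUS shows 50-99% or occlusion, or a TLR occurs, the subject is a failure at that visit and at all later visits*.
5. State that in the Kaplan-Meier analysis the first event takes precedence over Day 395 censoring of subjects classed as successes.
6. List fail-to-patent reversions separately, so that they can be queried with the core lab.

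With these changes F-M-P is a failure at 6 and 12 months, F-P-M is a failure at 12 months, and no sequence is a binary success or not evaluable after a Kaplan-Meier event.

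The cost is SAP wording and a programming change, with no new data. The downsides are that binary patency becomes slightly lower and that one false failing scan becomes permanent, as it already is under the Kaplan-Meier rule. The reversion listing makes that second effect visible.

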7.3 Data Analysis

The analysis population consists of all enrolled subjects who have signed the Informed Consent Form and have been treated with the study device.

Study endpoints will be summarized using descriptive statistics. Summary statistics for categorical variables will include frequency counts and percentages and for continuous variables mean, standard deviation, minimum, median and maximum.

Primary endpoints will be reported by rate and with a 95% confidence interval. The calculation of rates will be based on available data. Missing data will not be imputed.

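### SAP 6.5 fills in a missed 30-day or 6-month scan when the next scan is patent but drops the subject when it has failed, so the binary early ATK patency rates can be overstated

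*SAP*

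**What the plan says.** SAP 6.5 reports ATK primary patency at 30 days, 6 months and 12 months as a proportion of evaluable subjects. A subject is evaluable at a visit with a valid scan in its window ("23 - 37 days for 30 days, 150 - 210 days for 6 months, and 335 - 395 days for the 12 months"), with a failed last scan before it, or because "the subject should have had a TLR event before the upper limit of visit window". Three notes cover a missed or invalid scan:

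- Note a) looks forward. It takes a subject whose scan is missing, "yet the DUS result in the next visit is patent and the subject has no TLR by the next visit date". Such a person is put into the denominator on the favourable side; the note's wording is "then the subject is evaluable and will be counted as success".
- Note b) looks backward. It counts a failure if the scan is missing, "and the last DUS result prior to the respective visit indicates failure, and there is no DUS result on subsequent visits to indicate patency".
- Note c) takes the rest. If a subject has no TLR before the visit and "does not meet the conditions specified in a) and b) above, then the subject is not evaluable".

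A Kaplan-Meier analysis runs alongside: "In addition to the analyses that are proportion-based, survival analysis will be performed". SAP 7.2 (adjunctive treatments) and 7.3.2 (drug-coated balloon subjects) reuse the 6.5 definitions. Protocol 7.3 bases rates on available data and adds "Missing data will not be imputed". SAP 1.1 declares no departure from the protocol.

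**The concern.** No note carries a failed next scan back. Two subjects can have the same history up to a missed 6-month visit, and whether each is counted at 6 months is decided by what is found at 12 months. Later successes are added and later failures are removed. That is selection on a future outcome, and it operates even when scans are missed completely at random. In a single-arm study without a hypothesis test, the reported proportion is the result, so a rule that can push it only one way relative to even-handed rules deserves correction. The subgroup tables in SAP 7.2 and 7.3.2 inherit the rule with smaller denominators.

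**Working it through.** The documents give no patency rate, missed-scan rate or precision target, so there is no planned figure to reproduce. The check is the logic of the rule, then its size under stated assumptions.

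**1. Classification.** Take an ATK subject with no failed 30-day scan, no TLR by Day 210 and no valid 6-month scan.

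| Later finding | Note | 6-month status |
|---|---|---|
| 12-month scan patent, no TLR | a) | success |
| 12-month scan 50-99% or occluded | c) | not evaluable |
| TLR after Day 210 | c) | not evaluable |
| No valid 12-month scan, no TLR | c) | not evaluable |

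The same holds at 30 days, where Note b) cannot help because no earlier scan is scheduled. At 12 months no later visit is scheduled, so Note a) has nothing to act on.

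**2. Direction against symmetric rules.** Let N/D be the rate when no next scan is used, x the subjects added by Note a), and y the later failures dropped by Note c). The SAP rate is (N + x)/(D + x). It exceeds N/D whenever N < D and x > 0. It also exceeds (N + x)/(D + x + y), the rate when both kinds of next scan are used, whenever y > 0. No patency assumption is needed.

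**3. Size against true patency.** Assumed inputs: p1 = patency at the visit; p2 = patency at the next visit; m = share of scans missed, at random; q = share of missers with a valid next scan; k = share of failures at the visit already known through TLR or an earlier failed scan. Lost patency is taken not to return.

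SAP rate = [(1 − m)p1 + m·q·p2] / [(1 − m) + m·q·p2 + m·k(1 − p1)]

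This exceeds p1 only when k < q·p2/p1.

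At 6 months with p1 = 0.85, p2 = 0.70, m = 0.20:

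- k = 0, q = 1: (0.68 + 0.14)/(0.80 + 0.14) = 0.82/0.94 = 87.2%, bias +2.2 points.
- k = 0.5, q = 1: 0.82/(0.94 + 0.015) = 0.82/0.955 = 85.9%, bias +0.9.
- k = 0.5, q = 0.7: (0.68 + 0.098)/(0.80 + 0.098 + 0.015) = 0.778/0.913 = 85.2%, bias +0.2.
- k = 0.5, q = 0.6: (0.68 + 0.084)/(0.80 + 0.084 + 0.015) = 0.764/0.899 = 85.0%, bias about 0.

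The break-even k is 0.70/0.85 = 0.82 at q = 1, 0.58 at q = 0.7 and 0.49 at q = 0.6. Across m = 10, 20 and 30% with q = 1, the rate is 86.1, 87.2 and 88.5% at k = 0, and 85.4, 85.9 and 86.3% at k = 0.5. A simulation of one million subjects (m = 0.20, k = 0.4, q = 1) gave 86.2% against 86.1% from the formula.

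At 30 days with p1 = 0.97, p2 = 0.85, k = 0, q = 1: m = 0.10 gives 0.958/0.985 = 97.3% (+0.3), and m = 0.20 gives 0.946/0.970 = 97.5% (+0.5).

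**4. In whole subjects.** Of 175 ATK subjects, suppose 140 are scanned at 6 months (119 patent) and 35 are missed. Of those 35, 25 are patent and 10 failed at 12 months, none known earlier. The SAP gives 144/165 = 87.3%; scanned subjects only, 119/140 = 85.0%; both kinds of next scan, 144/175 = 82.3%.

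**5. Bounds.** For m = 0.20, k = 0.5, q = 1, the dropped share is 0.20 × (0.30 − 0.075) = 0.045, about 8 of 175. Counting all of them as failures gives 0.82/1.00 = 82.0%; counting all as successes gives 0.865/1.00 = 86.5%. The assumed truth of 85% lies between.

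**The case against.** Note a) is sound by itself: a patent later scan with no TLR implies patency at the missed visit. A failed later scan leaves the earlier status unknown, and calling it not evaluable fits a rule of available data. This stands, and it means the fault is selection, not misclassification.

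The Kaplan-Meier analysis keeps these subjects, so they do not vanish from the report. That also stands. But it dates the failure at the later scan or TLR, so such a subject is event-free at Day 210. It does not repair the early proportion.

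The effect is small beside sampling error: 1.96 × √(0.85 × 0.15/175) is about ±5.3 points for 175 subjects at 85%. That is fair and bears on severity, although a systematic shift does not appear in a confidence interval.

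The no-imputation sentence in Protocol 7.3 directly follows the primary-endpoint rule, so its reach to secondary endpoints can be argued. The passages still need to be reconciled.

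**Conclusion.** The one-sided rule is in the text, and nothing else in the SAP corrects it. The binary 30-day and 6-month ATK rates are higher than under either symmetric use of the next scan. Against true patency they can be overstated, provided k < q·p2/p1. Under the assumed inputs with 20% missed, the 6-month bias runs from +2.2 points to about zero; at 30 days it is at most about 0.5 points with 97% patency and 10-20% missed. Every rate here is an assumption.

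A reader might infer three stronger conclusions that the documents do not support:

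- That early patency is necessarily overstated. If many failures are already known, or few missers have a next scan, the bias vanishes or reverses.
- That COVID-19 makes it worse. The only COVID-19 provision, SAP 6.6, concerns late 12-month visits, no early missed-scan rate is given, and disruption would also lower q.
- That later failures should simply be counted as early failures. In the example that gives 82.0% against a true 85%, further off than the SAP rule's 85.9% or 87.2%.

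Severity is minor: one secondary, descriptive endpoint, with the 12-month proportion untouched by Note a).

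**What to change.** In SAP 6.5, keep subjects with a failed next scan or a later TLR in the 30-day and 6-month denominators. Report two bounds, one counting all of them as failures (lower) and one counting all as successes (upper), with neither as the main figure. Alternatively, make an interval-censored (Turnbull) estimate at Days 37 and 210 the main early patency figure. Subjects with no later scan remain unknown; count and show them, because the bounds need not cover the whole cohort if there are many. Apply the same rule in SAP 7.2 and 7.3.2. Reconcile Note a) with Protocol 7.3, and declare it in SAP 1.1 if it departs from the protocol.

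The cost is SAP wording and minor programming, with no new data. The early rates would appear as a range or be slightly less favourable.

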7.2 Primary and Secondary Endpoints for Different Adjunctive Treatments

The two primary endpoints will be analyzed for different adjunctive treatments ('Prior to UltraScoreTM Use', 'After UltraScoreTM Use' and both combined) for ATK, BTK and All UltraScoreTM subjects. The secondary endpoints (TLR, Major Amputation and Primary Patency) will be analyzed for different adjunctive treatments ('After UltraScoreTM Use') for ATK, BTK and All UltraScoreTM subjects. The endpoints and statistical methods will be similar to section 5 and section 6.

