7.5 Evaluation of Secondary Endpoints

The following secondary endpoints will be reported at the index procedure or through 12 months at these time points: 30 days, 6 months, and 12 months.

After UltraScore[™] Focused Force PTA balloon:

• Rate of bail-out stenting due to dissection

Through follow-up (30 days, 6 and 12 months):

- Freedom from TLR
- Freedom from major amputation (above the ankle)
- Improved clinical measures from baseline (ABI, Rutherford)
- Primary patency for ATK subjects only (as measured by DUS core lab; a PSVR ≥2.5 suggests 50% restenosis)

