3.4 Study Procedure

All subjects will undergo a clinical evaluation at screening (prior to index procedure); after consent is voluntarily obtained, study subjects will be treated with the UltraScoreTM Focused Force PTA balloon per the site's standard of care and adhering to the IFU. Examinations, evaluations, procedural preparation, angiography, treatment and hospital discharge procedures will be conducted per the study site's standard of care.

Investigators are able to treat One (1) lesion per patient in this study. If a subject has multiple eligible lesions, the investigator may use his or her medical judgment as to which becomes the study target lesion. Standard of care treatment of non-target lesions is allowed.

Subjects with treated ATK lesions will undergo clinical evaluations with a Duplex Ultrasound (DUS) performed at 30 days, 6 and 12 months post-index procedure.

Subjects with treated BTK lesions will undergo clinical evaluations performed at 30 days, and 6 and 12 months post-index procedure. DUS is not required for subjects with a treated BTK lesion for this study.

Lesions that cross from ATK to BTK may not be treated as the study target lesion. Diffuse lesions will be considered separate lesions if there is 2 cm of healthy tissue between lesions.

Angiographic imaging of the target lesion is captured at Baseline cine-run, Pre-UltraScore[™] adjunctive treatment cine-run (if performed), UltraScore[™] balloon inflation(s), Post UltraScore[™] balloon inflation(s) cine run, and Post UltraScore[™] adjunctive treatment cine-run (if performed). Angiographic imaging is also done at Re-Intervention visit. Major flow limiting dissections are collected and reporting is restricted to grades D, E, and F per the National Heart, Lung, and Blood Institute (NHLBI).

Adjunctive treatment of the target lesion before or after use of the UltraScore[™] balloon as part of standard care procedures is allowed. Bail out stenting and stenting of non-study lesions is acceptable at any time.

Collection and reporting of AEs/SAEs will be limited to those events that are device and/or procedure related and reporting will begin immediately following subject enrollment, during the index procedure.

If an angiographically acceptable result cannot be obtained after two inflations of the UltraScoreTM balloon (>30% residual stenosis), the subject should be considered a treatment failure.

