An overview of the study visit schedules is shown in Table 1, which summarizes the schedule for subject treatment and evaluation.

Table 1: Follow-up Schedule a	nd Testing Requirements fo	r Enrolled Subjects
ruore in ronow up senedure u	ita Testing Requirements io	i Emoned Subjeets

	Screening / Index Procedure / Discharge	30 Days (±7 days)	6 Months (±30 days)	12 Months (±30 days)
Informed Consent	\checkmark			
Demographics / Medical History	\checkmark			
Physical Examination (Clinical Assessments)	\checkmark			
Rutherford (Category and Grade)	\checkmark	~	\checkmark	~
Resting ABI (Treated Limb only)	\checkmark	~	\checkmark	~
Anticoagulation/Anti-platelets	\checkmark	~	\checkmark	~
Eligibility Criteria	\checkmark			
Angiographic Image Collection	\checkmark			
Duplex Ultrasound§		\checkmark	\checkmark	\checkmark
TLR Assessment*		\checkmark	\checkmark	\checkmark
Adverse Event Assessment	\checkmark	\checkmark	\checkmark	\checkmark

§ATK subjects only

*Collect angiographic images for TLR/TVR

4 Analysis Set

Enrolled: All subjects who have signed the Informed Consent Form (ICF) and the UltraScoreTM balloon was introduced into the subject.

Intent-to-Treat (ITT): All enrolled subjects who have signed the ICF and were treated with the study device.

There is no formal statistical hypothesis for this study. Baseline characteristics, demographics, primary endpoints, secondary endpoints, other analyses and subgroup analyses will be based on the ITT population.

5 Statistical Analysis of the Primary Endpoints

The proportion of subjects with optimal PTA results and technical success will be reported with frequency counts, percentages and 95% confidence intervals (CI) for the percentages from exact binomial test.

5.1 To Achieve Optimal PTA Results (≤30% residual stenosis, without major flow limiting dissection)

The residual stenosis (Interpolated %DS) and major flow limiting dissection (Dissection) will be used from the Angio Core Lab CRF page (Image Findings-After UltraScore[™] Balloon QVA). If Angio Core Lab data is missing use the site data (site reported residual stenosis after inflations (%) from the Study Device CRF page and flow limiting dissection (D to F) from the Procedure Overview CRF page).

An optimal PTA result will be analyzed by subject as a binary endpoint based on the following definition:

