7.3.2 Assessment of Secondary Endpoints for subjects with DCB used at baseline

Freedom from TLR and major amputation will be separately reported for ATK, BTK and All UltraScore[™] subjects with DCB used at baseline either before or after ultrascore.

Primary patency will be reported for ATK subjects with DCB used at baseline either before or after ultrascore.

Secondary endpoints and evaluable subjects are as defined in section 6.2, 6.3 and 6.5, respectively, with an additional requirement that the subjects have had DCB at index procedure.

7.3.3 Assessment of death for subjects with DCB used at baseline either before or after ultrascore

Freedom from death will be reported at 30 days, 6 months, and 12 months using data from 'Subject Disposition' CRF page.

Evaluable subjects: To be included in the denominator at a particular visit, the subject should have had DCB as adjunctive treatment either before or after Ultrascore and been followed-up beyond the beginning of the lower end of the respective visit window (23 days for 30 days, 150 days for 6 months, and 335 days for the 12 months) or the subject should have had died before the upper limit of visit window (37 days for 30 days, 210 days for 6 months, and 395 days for the 12 months).

Death duration = (Date of Death - Date of Index Procedure).

8 Statistical Analyses of Adverse Events and Device Deficiencies

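### SAP 7.2 (and, by loose wording, SAP 7.1) extends primary patency to below-the-knee and All subjects, although the endpoint is defined and scanned above the knee only

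*SAP*

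**What the plan says.** SAP 7.2 covers results by adjunctive treatment. For adjuncts given after the study balloon it says "The secondary endpoints (TLR, Major Amputation and Primary Patency) will be analyzed for different adjunctive treatments", and the groups and methods follow: "for ATK, BTK and All UltraScoreTM subjects. The endpoints and statistical methods will be similar to section 5 and section 6". No exception is made for patency. SAP 7.1 is looser still: it presents the primary and secondary endpoints descriptively for ATK and BTK subjects, again without an exception.

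Everywhere else patency belongs to ATK subjects. Protocol 7.5 lists it as "Primary patency for ATK subjects only (as measured by DUS core lab; a PSVR ≥2.5 suggests 50% restenosis"; Protocol 4.2 and SAP 2.2.2 carry the same restriction. The heading of SAP 6.5 reads "Primary Patency for ATK subjects only (as measured by DUS Core Lab". SAP 7.3.2 reports TLR and amputation for ATK, BTK and All, and then gives patency its own sentence: "Primary patency will be reported for ATK subjects with DCB used at baseline either before or after ultrascore".

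The visit schedule matches the restriction. SAP 3.4 says "DUS is not required for subjects with a treated BTK lesion for this study", and the DUS row of SAP Table 1 is footnoted "ATK subjects only", as it is in Protocol Appendix B. SAP 1.1 declares no changes from the protocol.

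**The concern.** A programmer who follows 7.2 literally would produce patency for a group that has no scheduled imaging. The 6.5 evaluability rule was written for subjects who are scanned. Applied to subjects who are not, it admits re-interventions and leaves out subjects who do well. At stake are the patency figures by adjunct. Strata with different mixes of ATK and BTK lesions could look different for reasons unrelated to the adjunct. The study has no hypothesis test and exists to give physicians descriptive outcome data, patency included, so these tables are part of its output.

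**Working it through.** The documents give no patency or TLR rate, so there is no planned figure to reproduce. The direction of the effect follows from the rules; its size needs assumed rates.

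**Step 1. Who is evaluable in the proportion-based analysis (SAP 6.5).** A subject enters the denominator through a valid DUS in the window, through an earlier DUS showing failure, or by the third route: "or the subject should have had a TLR event before the upper limit of visit window". Note a) needs a later patent DUS and note b) an earlier failed one. Under note c) a subject with none of these and no TLR is not evaluable. A BTK subject with no DUS therefore has one way in, a TLR, and a TLR is a failure.

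**Step 2. Formulas.** Let S be the ATK successes, N the evaluable ATK subjects, and T the BTK subjects with a TLR and no DUS.

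- BTK patency = 0/T, undefined if T = 0.
- All patency = S/(N + T).
- Fall against ATK = S/N − S/(N + T) = (S/N) × T/(N + T), which is positive whenever S and T are both above zero.

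**Step 3. Size over the whole cohort.** The planned cohorts are about 175 ATK and 175 BTK (SAP 3.3). Assumed: 90% of ATK subjects evaluable (N = 158), of whom about 80% are patent (S = 126), so ATK patency is 126/158 = 79.7%.

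| Assumed BTK TLR | T | BTK patency | All patency | Fall (points) |
|---|---|---|---|---|
| 5% | 9 | 0/9 | 126/167 = 75.4% | 4.3 |
| 10% | 18 | 0/18 | 126/176 = 71.6% | 8.2 |
| 15% | 26 | 0/26 | 126/184 = 68.5% | 11.3 |
| 20% | 35 | 0/35 | 126/193 = 65.3% | 14.5 |

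Varying ATK evaluability over 80–100%, ATK patency over 60–90% and BTK TLR over 5–20%, the fall runs from 2.9 points (105/175 = 60.0% to 105/184 = 57.1%) to 18.0 points (126/140 = 90.0% to 126/175 = 72.0%). With N = 150, 75% patency and BTK TLR of 10, 20 or 30%:

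- 112.5/167.5 = 67.2%, a fall of 7.8 points
- 112.5/185 = 60.8%, a fall of 14.2 points
- 112.5/202.5 = 55.6%, a fall of 19.4 points

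**Step 4. Effect between strata.** SAP 7.2 reports by adjunct, so the lesion mix matters. Take two hypothetical adjuncts with the same assumed ATK patency (75%) and BTK TLR (20%), and all ATK subjects evaluable.

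- 80 ATK and 20 BTK: 60/(80 + 4) = 71.4%
- 20 ATK and 80 BTK: 15/(20 + 16) = 41.7%

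The gap of 29.7 points comes from lesion location alone.

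**Step 5. Off-schedule DUS.** DUS is not required in BTK subjects, but it is not forbidden. Start from the 10% row, which leaves 157 TLR-free BTK subjects. If 10% of them (16) had a core-lab DUS and 13 were patent, BTK patency is 13/(18 + 16) = 38.2% and All is (126 + 13)/(158 + 34) = 72.4%, still below 79.7%.

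**Step 6. Kaplan-Meier analysis.** SAP 6.5 also calls for Kaplan-Meier estimates, and 7.2 carries the section 6 methods over. There, subjects with a missing patency endpoint are censored at their last study day, so TLR-free BTK subjects stay in the risk set. The BTK curve is then freedom from TLR. With 175 per cohort, everyone followed to about 12 months, and ATK patency 80% (35 failures):

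- BTK TLR 10% (18 events): All = 1 − 53/350 = 84.9%
- BTK TLR 20% (35 events): All = 1 − 70/350 = 80.0%
- BTK TLR 30% (52 events): All = 1 − 87/350 = 75.1%

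So All can lie above, at or below the ATK value.

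**The case against.** The best defence is that 7.2 says its endpoints and methods are similar to those of section 6, and the section 6 endpoint is ATK-only by name, definition and output. On that reading the three groups apply only where an endpoint is defined for them, and no BTK subject ever enters. The reading is reasonable and may be what was intended. It does not settle the matter: the sentence itself names BTK and All, and 7.3.2 shows that the SAP separates patency explicitly when it means to. Two programmers could fairly build different tables from 7.2.

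Three stronger conclusions are tempting, and the documents do not support them.

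- A reader might infer that BTK patency will be 0% in every stratum. It is undefined where no BTK subject has had a TLR, which is most plausible at 30 days or in small strata, and an off-schedule patent DUS lifts it above zero.
- A reader might infer that All patency is always pulled down, so that adjuncts used more below the knee always look worse. That holds for the proportions when BTK subjects have no DUS, but not for Kaplan-Meier.
- A reader might infer that the study's patency result is biased. SAP 6.5 and 7.3.2 are explicitly ATK-only.

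**Conclusion.** SAP 7.2 contradicts the ATK-only definition of patency in Protocol 4.2 and 7.5 and in SAP 2.2.2, 6.5 and 7.3.2; SAP 7.1 shares the loose wording for BTK. Programmed as written, 7.2 yields BTK and All figures that are not patency in either planned analysis. For the proportions without off-schedule DUS the downward direction is certain whenever a BTK subject has a TLR and ATK has any success. The size, about 3 to 19 points, is an illustration on assumed whole-cohort rates; within a stratum it depends on the BTK share and TLR rate and can be larger. For Kaplan-Meier the direction is open. Because the analysis is a descriptive subgroup analysis and the main patency result is untouched, the defect is minor to moderate. It is still worth correcting, since the correction costs almost nothing.

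**What to change.** In SAP 7.2, state that TLR and major amputation are analysed by adjunctive treatment for ATK, BTK and All subjects, and primary patency by adjunctive treatment for ATK subjects only. This follows the split already made in 7.3.2. Add the same ATK-only clarification for patency to SAP 7.1, and omit BTK and All patency from the corresponding output tables. The cost is a sentence in each of two sections and fewer table columns; no data collection changes.
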